7.3 Subject Population(s) for Analysis

Each participant who received the study drug will be included in the primary analysis regardless of study withdrawal for any reason. In the event of any study withdrawals, for any secondary analysis, we will examine the sensitivity of our results to the exclusion of patients who withdrew.

8 Safety and Adverse Events

8.1 Definitions

Unanticipated Problems Involving Risk to Subjects or Others (UPIRTSO)

Any unanticipated problem or adverse event that meets the following three criteria:

- **Serious**: Serious problems or events that results in significant harm, (which may be physical, psychological, financial, social, economic, or legal) or increased risk for the subject or others (including individuals who are not research subjects). These include: (1) death; (2) life threatening adverse experience; (3) hospitalization - inpatient, new, or prolonged; (4) disability/incapacity - persistent or significant; (5) birth defect/anomaly; (6) breach of confidentiality and (7) other problems, events, or new information (i.e. publications, DSMB reports, interim findings, product labeling change) that in the opinion of the local investigator may adversely affect the rights, safety, or welfare of the subjects or others, or substantially compromise the research data, **AND**
- **Unanticipated**: (i.e. unexpected) problems or events are those that are not already described as potential risks in the protocol, consent document, not listed in the Investigator's Brochure, or not part of an underlying disease. A problem or event is "unanticipated" when it was unforeseeable at the time of its occurrence. A problem or event is "unanticipated" when it occurs at an increased frequency or at an increased severity than expected, **AND**
- **Related**: A problem or event is "related" if it is possibly related to the research procedures.

Adverse Event

An untoward or undesirable experience associated with the use of a medical product (i.e. drug, device, biologic) in a patient or research subject.

Serious Adverse Event

Adverse events are classified as serious or non-serious. Serious problems/events can be well defined and include;

- death
- life threatening adverse experience
- hospitalization
- inpatient, new, or prolonged; disability/incapacity
- persistent or significant disability or incapacity
- birth defect/anomaly

and/or per protocol may be problems/events that in the opinion of the sponsor-investigator may have adversely affected the rights, safety, or welfare of the subjects or others, or substantially compromised the research data.

All adverse events that do not meet any of the criteria for serious, should be regarded as **non-serious adverse events**.

Adverse Event Reporting Period

For this study, the study treatment follow-up period is defined as the last scheduled visit.

Preexisting Condition

A preexisting condition is one that is present at the start of the study. A preexisting condition should be recorded as an adverse event if the frequency, intensity, or the character of the condition worsens during the study period.

General Physical Examination Findings

At screening, any clinically significant abnormality should be recorded as a preexisting condition. At the end of the study, any new clinically significant findings/abnormalities that meet the definition of an adverse event must also be recorded and documented as an adverse event.

Post-study Adverse Event

All unresolved adverse events should be followed by the sponsor-investigator until the events are resolved, the subject is lost to follow-up, or the adverse event is otherwise explained. At the last scheduled visit, the sponsor-investigator should instruct each subject to report, to the sponsor-investigator, any subsequent event(s) that the subject, or the subject's personal physician, believes might reasonably be related to participation in this study.

Abnormal Laboratory Values

Any clinical laboratory abnormality that can reasonably be related to the administration of dupilumab should be documented as an adverse event.

Hospitalization, Prolonged Hospitalization or Surgery

Hospitalization, prolonged hospitalization, or surgery is to be reported as an adverse event if it can reasonably be related to use of dupilumab.

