5.1.3 Pharmacokinetics

Absorption: Following an initial subcutaneous (SC) dose of 600 mg, dupilumab reached peak mean \pm SD concentrations (C_{max}) of 70.1 \pm 24.1 mcg/mL by approximately 1 week post dose. Steady-state concentrations were achieved by Week 16 following the administration of 600 mg starting dose and 300 mg dose either weekly (twice the recommended dosing frequency) or every other week. Across clinical trials, the mean \pm SD steady-state trough concentrations ranged from 73.3 \pm 40.0 mcg/mL to 79.9 \pm 41.4 mcg/mL for 300 mg administered every 2 weeks and from 173 \pm 75.9 mcg/mL to 193 \pm 77.0 mcg/mL for 300 mg administered weekly. The bioavailability of dupilumab following a SC dose is estimated to be 64%.

Distribution: The estimated total volume of distribution was approximately 4.8 ± 1.3 L.

Elimination: The metabolic pathway of dupilumab has not been characterized. As a human monoclonal IgG4 antibody, dupilumab is expected to be degraded into small peptides and amino acids via catabolic pathways in the same manner as endogenous IgG. After the last steady-state dose of 300 mg Q2W or 300 mg QW dupilumab, the median times to non-detectable concentration (<78 ng/mL) are 10 and 13 weeks, respectively.

Dose Linearity: Dupilumab exhibited nonlinear target-mediated pharmacokinetics with exposures increasing in a greater than dose-proportional manner. The systemic exposure increased by 30-fold when the dose increased 8-fold following a single dose of dupilumab from 75 mg to 600 mg (i.e., 0.25times to 2-times the recommended dose).

Weight: Dupilumab trough concentrations were lower in subjects with higher body weight.

Immunogenicity: Development of antibodies to dupilumab was associated with lower serum dupilumab concentrations. A few subjects who had high antibody titers also had no detectable serum dupilumab concentrations.

Specific Populations:

Geriatric Patients

In subjects who are 65 years and older, the mean \pm SD steady-state trough concentrations of dupilumab were 69.4 ± 31.4 mcg/mL and 166 ± 62.3 mcg/mL, respectively, for 300 mg administered every 2 weeks and weekly. No dose adjustment in this population is recommended.

Renal or Hepatic Impairment

No formal trial of the effect of hepatic or renal impairment on the pharmacokinetics of dupilumab was conducted.

Drug Interaction Studies: Drug interaction studies have not been conducted with dupilumab.

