8.2 Recording of Adverse Events

At each contact with the subject, the study team will seek information on adverse events by specific questioning and, as appropriate, by examination. Information on all adverse events should be recorded immediately in the source document, and also in the appropriate adverse event section of the case report form (CRF). All clearly related signs, symptoms, and abnormal diagnostic, laboratory or procedure results will be recorded in the source document.

All adverse events occurring during the study period will be recorded. The clinical course of each event should be followed until resolution, stabilization, or until it has been ultimately determined that the study treatment or participation is not the probable cause. Serious adverse events that are still ongoing at the end of the study period must be followed up, to determine the final outcome. Any serious adverse event that occurs during the Adverse Event Reporting Period and is considered to be at least possibly related to the study treatment or study participation should be recorded and reported immediately.

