8.3.1 Sponsor-Investigator reporting: notifying the Mayo IRB

The Principal Investigator and/or Investigators will report, as soon as possible, but no later than 5 working days after first learning of the problem/event, to the Mayo Clinic IRB any UPIRTSOs and Non-UPIRTSOs according to the Mayo Clinic IRB Policy and Procedures.

Documentation of adverse events will include the following information collected in the adverse event section of the case report form (and entered into the research database):

- Subject's name:
- Medical record number:
- Disease:
- The date the adverse event occurred:
- Description of the adverse event:
- Relationship of the adverse event to the research:
- If the adverse event was expected:
- The severity of the adverse event (defined by a severity scale):
- If any intervention was necessary:
- Resolution (was the incident resolved spontaneously, or after discontinuing treatment):
- Date of Resolution:

The Principal Investigator and/or Investigators will review all adverse event reports to determine if specific reports need to be made to the IRB and FDA. The Principal Investigator and/or Investigators will sign and date the adverse event report when it is reviewed. For this protocol, only directly related SAEs/UPIRTSOs will be reported to the IRB.

Page 23 of 29

[name]

[name]

[name], DO

CONFIDENTIAL

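### Section 8.1 ties adverse-event status for hospitalisation, surgery and laboratory abnormalities to a judgement of drug relatedness, and 8.3.1 sets a narrower IRB threshold than 8.1 and 8.2 do

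*Combined protocol and SAP*

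**What the plan says.** **Which events count (8.1).** The general definition of an adverse event is "An untoward or undesirable experience associated with the use of a medical product"; it does not say whether the association is one of timing or of cause. Two later paragraphs of 8.1 are specific:

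- Laboratory values: "Any clinical laboratory abnormality that can reasonably be related to the administration of dupilumab should be documented as an adverse event".
- Admissions and operations: a hospitalisation, a prolonged one, or surgery "is to be reported as an adverse event if it can reasonably be related to use of dupilumab".

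The list of serious events in 8.1 includes hospitalisation and attaches no relatedness condition. Another paragraph of 8.1 treats a condition already present at study start as an adverse event once it worsens, whatever the cause.

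**What is recorded (8.2).** "All adverse events occurring during the study period will be recorded". Each event is then followed until it resolves, stabilises, or treatment is found not to be the probable cause. Serious events that are at least possibly related are to be reported at once; the recipient is not named.

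**What goes to the IRB (8.3.1).** The section opens by sending UPIRTSOs and non-UPIRTSOs alike to the IRB, as IRB policy directs. It lists relationship to the research as a field in the adverse-event documentation. It closes by saying that "only directly related SAEs/UPIRTSOs will be reported to the IRB". In the UPIRTSO definition of 8.1, an event counts as related "if it is possibly related to the research procedures".

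**The concern.** An adverse-event record normally takes in every untoward event and grades causality afterwards. Here, for three kinds of event, the causality judgement comes first and decides whether there is a record at all. All participants have cholestatic liver disease, so the disease is a ready alternative explanation for a change in AST, ALT or INR, or for an admission. There is no placebo arm (5.3), so the investigator's attribution cannot be compared with a background rate.

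The record also feeds other parts of the plan. Section 3.6 relies on examination and laboratory testing to assess safety in this population, and 8.6 relies on the number and type of serious events. Section 8 sets up no monitoring board and 8.3.2 says the study is not under an IND, which makes the IRB the main outside recipient of safety reports. The closing sentence of 8.3.1 narrows what it receives.

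**Working it through.** The plan gives no adverse-event rate and no power calculation (7.1), so there is no figure of its own to reproduce. The check is mainly a comparison of texts.

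**Step 1. Relatedness thresholds in Section 8**

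| Place | Purpose | Threshold |
|---|---|---|
| 8.1, laboratory values; hospitalisation or surgery | to be an adverse event | *reasonably* related |
| 8.1, worsening preexisting condition | to be an adverse event | none |
| 8.1, list of serious events | to be serious | none |
| 8.2, general rule | to be recorded | none, once it is an adverse event |
| 8.2, serious events | immediate report | at least *possibly* related |
| 8.1, UPIRTSO definition | to be related | *possibly* related |
| 8.3.1, opening | report to IRB | none stated; per IRB policy |
| 8.3.1, close | report to IRB | *directly* related (undefined) |

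There are three different words for relatedness, and two IRB rules within 8.3.1 that do not match.

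**Step 2. Can an event be lost from the record?** Four cases:

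1. Liver disease worsens and leads to an admission judged unrelated to dupilumab. The preexisting-condition rule records the worsening; the hospitalisation rule, on its natural reading, does not make the admission an adverse event. The two rules pull apart.
2. A laboratory abnormality appears that is new and not a worsening of a known condition, and is judged unrelated. No 8.1 rule clearly makes it an adverse event. If it is one of the scheduled CBC, AST, ALT or INR tests (screening, weeks 6, 12 and 18), the value is kept in source documents and the EMR, but 3.7 does not put it directly on the CRF.
3. An admission or surgery has no link to a preexisting condition and is judged unrelated. It can be left out.
4. Any of these is judged reasonably related. It is recorded.

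So cases 2 and 3 are exposed and case 1 is partly protected.

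**Step 3. Can a reportable event be missed by the IRB?** A UPIRTSO must be serious, unanticipated and related, with related meaning possibly related. An event that meets all three but is not judged directly related is a UPIRTSO under 8.1, yet falls outside the closing sentence of 8.3.1.

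**Step 4. Illustration of size (hypothetical).** n = 12 (3.2). Exact (Clopper-Pearson) 95% limits:

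- 0/12: upper limit = 1 − 0.025^(1/12) = 26.5%; lower limit 0.
- 1/12 = 8.3%: lower limit = 1 − 0.975^(1/12) = 0.2%; the upper limit solves (1−p)^12 + 12p(1−p)^11 = 0.025, giving 38.5%.

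Let p be the true per-patient risk of an event and f the share judged related. Both are assumptions. The chance that at least one patient has a recorded event is 1 − (1 − p·f)^12:

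| p | f = 1 | f = 0.5 | f = 0.25 |
|---|---|---|---|
| 10% | 0.72 | 0.46 | 0.26 |
| 20% | 0.93 | 0.72 | 0.46 |
| 30% | 0.99 | 0.86 | 0.61 |

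A relatedness condition can only lower the count. Nothing in the documents fixes p or f.

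**The case against.** The strongest reply is that the safety data are better protected than the two sentences suggest. Much of it stands.

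- **Hepatic events vanish.** A reader might infer this, but the text does not support it. Worsening of a preexisting condition is an adverse event whatever its cause, and every participant has liver disease. Scheduled laboratory values and their interpretation are kept (3.7). What may be lost is the adverse-event entry, not the value.
- **8.1 flatly contradicts 8.2.** This is too strong. The rule in 8.2 covers adverse events, and 8.1 defines those. One sentence in 8.2 also speaks of laboratory results that are clearly related. The list of serious events classifies adverse events; it does not say that every admission is one. The wording in 8.1 is also *if*, not *only if*. The conflict is partial, though the restrictive reading of the hospitalisation sentence is the natural one.
- **Any possibly related serious event is a UPIRTSO.** It is not; it must also be unanticipated.
- **Hepatic impairment was never studied.** Section 5.1.3 says only: "No formal trial of the effect of hepatic or renal impairment on the pharmacokinetics of dupilumab was conducted". That is a statement about pharmacokinetics and cannot carry a claim about safety.
- **The two IRB sentences may agree in practice.** The opening one is qualified by an IRB policy that is not in the documents, so how far they differ is partly unknown. IRB reporting also does not determine what is recorded, so this inconsistency is not evidence of undercounting.

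None of this removes the exposed cases: new laboratory abnormalities, and admissions or surgery judged unrelated.

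**Conclusion.** The point holds in a limited form. For laboratory abnormalities, hospitalisation and surgery, 8.1 conditions adverse-event status on relatedness to dupilumab. Followed as written, this can keep unrelated-judged events out of the adverse-event record in a 12-patient trial with no comparison group. The direction is undercounting. The size is unknown: 0/12 against 1/12 is arithmetic on one hypothetical omission, and the 0/12 interval itself contains 8.3%. The conclusion assumes that staff read *if* as a condition for recording.

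Separately, Section 8 gives the IRB threshold inconsistently, so that a serious, unanticipated, possibly related event could go unreported. How often depends on IRB policy, which the documents do not include.

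The efficacy analysis is untouched and there is no primary safety endpoint (3.6). The issue should be corrected because the planned safety assessment rests on this record.

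**What to change.** - **8.1:** remove the two relatedness conditions, so that every hospitalisation, surgery and clinically significant laboratory abnormality is recorded as an adverse event. Keep relatedness as the separate field that 8.3.1 already lists.
- **7.2:** add a table of all adverse events and, beside it, those judged related. The section specifies no such table now.
- **8.3.1:** reconcile the opening and closing IRB sentences with each other, with the possibly-related standard in 8.1 and 8.2, and with the cited IRB policy. Either define *directly related* or drop it.

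The cost is a wording amendment and a few more adverse-event forms for 12 patients. Some will describe disease-related events, which the relatedness field will identify.

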8.2 Recording of Adverse Events

At each contact with the subject, the study team will seek information on adverse events by specific questioning and, as appropriate, by examination. Information on all adverse events should be recorded immediately in the source document, and also in the appropriate adverse event section of the case report form (CRF). All clearly related signs, symptoms, and abnormal diagnostic, laboratory or procedure results will be recorded in the source document.

All adverse events occurring during the study period will be recorded. The clinical course of each event should be followed until resolution, stabilization, or until it has been ultimately determined that the study treatment or participation is not the probable cause. Serious adverse events that are still ongoing at the end of the study period must be followed up, to determine the final outcome. Any serious adverse event that occurs during the Adverse Event Reporting Period and is considered to be at least possibly related to the study treatment or study participation should be recorded and reported immediately.

8.3 Reporting of Serious Adverse Events and Unanticipated Problems

When an adverse event has been identified, the study team will take appropriated action necessary to protect the study participant and then complete the Study Adverse Event Worksheet and log. The sponsor-investigator will evaluate the event and determine the necessary follow-up and reporting required.

8.3.1 Sponsor-Investigator reporting: notifying the Mayo IRB

The Principal Investigator and/or Investigators will report, as soon as possible, but no later than 5 working days after first learning of the problem/event, to the Mayo Clinic IRB any UPIRTSOs and Non-UPIRTSOs according to the Mayo Clinic IRB Policy and Procedures.

Documentation of adverse events will include the following information collected in the adverse event section of the case report form (and entered into the research database):

- Subject's name:
- Medical record number:
- Disease:
- The date the adverse event occurred:
- Description of the adverse event:
- Relationship of the adverse event to the research:
- If the adverse event was expected:
- The severity of the adverse event (defined by a severity scale):
- If any intervention was necessary:
- Resolution (was the incident resolved spontaneously, or after discontinuing treatment):
- Date of Resolution:

The Principal Investigator and/or Investigators will review all adverse event reports to determine if specific reports need to be made to the IRB and FDA. The Principal Investigator and/or Investigators will sign and date the adverse event report when it is reviewed. For this protocol, only directly related SAEs/UPIRTSOs will be reported to the IRB.

Page 23 of 29

[name]

[name]

[name], DO

CONFIDENTIAL

8.3.2 Sponsor-Investigator reporting: Notifying the FDA

This protocol is not being conducted under an FDA investigational new drug application.

8.4 Unmasking/Unblinding Procedures

This is an open-label pilot investigation. Unmasking and unblinding procedures are not applicable.

8.5 Stopping Rules

This investigation is of low risk to study subjects. Stopping or interruption of the study may be necessary if a significant number of study participants develop unexpected clinical flaring or significant worsening that appears temporally linked with dupilumab administration.

8.6 Medical Monitoring

It is the responsibility of the Principal Investigator to oversee the safety of the study at his/her site. This safety monitoring will include careful assessment and appropriate reporting of adverse events as noted above, as well as the construction and implementation of a site data and safety-monitoring plan (see section 10 "Study Monitoring, Auditing, and Inspecting"). Medical monitoring will include a regular assessment of the number and type of serious adverse events.

9 Data Handling and Record Keeping

9.1 Confidentiality

Information about study subjects will be kept confidential and managed according to the requirements of the Health Insurance Portability and Accountability Act of 1996 (HIPAA). Those regulations require a signed subject authorization informing the subject of the following:

- What protected health information (PHI) will be collected from subjects in this study
- Who will have access to that information and why
- Who will use or disclose that information
- The rights of a research subject to revoke their authorization for use of their PHI

9.2 Source Documents

Source data is all information, original records of clinical findings, observations, or other activities in a clinical trial necessary for the reconstruction and evaluation of the trial. Source data are contained in source documents. Examples of these original documents, and data records include: hospital records, clinical and office charts, laboratory notes, memoranda, subjects'

diaries or evaluation checklists, pharmacy dispensing records, recorded data from automated instruments, copies or transcriptions certified after verification as being accurate and complete, microfiches, photographic negatives, microfilm or magnetic media, x-rays, subject files, and records kept at the pharmacy, at the laboratories, and at medico-technical departments involved in the clinical trial.

9.3 Case Report Forms

All data requested on the Case Report Form (CRF) will be recorded for each participant. A standardized CRF will be generated by REDCap. All missing data will be explained. If a space on the CRF is left blank because the question was not asked, "N/D" will be recorded. If the item is not applicable to the individual case, "N/A" will be recorded. All entries will be printed legibly in black ink. If any entry error has been made, a single straight line through the incorrect entry will be drawn and the correct data will be written above it. All such changes will be initialed and dated. Errors will not be erased or whited-out. For clarification of illegible or uncertain entries, a clarification will be printed above the item, then initialed and dated. If the reason for the correction is not clear or needs additional explanation, details to justify the correction will be neatly included.

Data Management

Study data will be collected and managed using REDCap electronic data capture tools hosted at the Mayo Clinic. REDCap (Research Electronic Data Capture) is a secure, web-based application designed to support data capture for research studies, providing 1) an intuitive interface for validated data entry; 2) audit trails for tracking data manipulation and export procedures; 3) automated export procedures for seamless data downloads to common statistical packages; and 4) procedures for importing data from external sources.

Data Processing

All study data will be stored and analyzed at Mayo Clinic in Florida using the REDCap electronic data capture tool.

Data Security and Confidentiality

All source documents including clinical findings, observations or other activities will be stored in a REDCap database that will be designed by the Statistician. Access to the REDCap database will be limited to the Principal Investigator, Investigators, and Statistician.

Data Quality Assurance

Once the study is completed the Principal Investigator will randomly select 3 participants and compare the data documented for each on the CRF with what is entered into the REDCap database. If there is any discrepancy, the Principal Investigator and/or Investigators will cross-reference all 12 patients to ensure accuracy.

Data Clarification Process

For any data query the Principal Investigator and Investigators will meet to clarify the data queried and make corrections based on consensus.

